Appendix 1a Schedule of Activities

- ⁱ A complete physical examination includes evaluation of the head, eyes, ears, nose, and throat, and the cardiovascular, dermatological, musculoskeletal, respiratory, gastrointestinal, and neurological systems. Record abnormalities observed at baseline on the General Medical History and Baseline Conditions eCRF. At subsequent visits, record new or worsened clinically significant abnormalities on the Adverse Events eCRF.
- ^j Perform a limited, symptom-directed physical examination within 96 hours prior to dosing at specified timepoints, and as clinically indicated. Changes from baseline abnormalities should be recorded in patient notes. New or worsened clinically significant abnormalities should be recorded as adverse events on the Adverse Event eCRF. (See Section 4.5.3)
- ^k Includes any medication (e.g., prescription drugs, vaccines, over-the-counter drugs, herbal or homeopathic remedies, nutritional supplements) used by the patient from 7 days prior to screening until the study completion/discontinuation visit. At each post-screening visit, changes to current medications or new medications used since the last documentation of medications will be recorded.
- ^l Hematology consists of CBC, including RBC count, hemoglobin, hematocrit, WBC count with differential (neutrophils, lymphocytes, eosinophils, monocytes, basophils, and other cells), and platelet count.
- ^m Serum chemistry includes glucose, BUN or urea, creatinine, sodium, potassium, magnesium, chloride, bicarbonate or total CO₂, calcium, phosphorus, total and direct bilirubin, ALT, AST, alkaline phosphatase, LDH, total protein, and albumin. Serum will be collected every 3 cycles to test thyroid function. HBV and HCV will be tested as clinically indicated. CRP from screening and Cycle 3, Day 1 will be tested centrally from previously obtained samples; no additional samples will be needed.
- ⁿ All women of childbearing potential (including those who have had a tubal ligation) must have a negative serum pregnancy test at screening (within 14 days prior to Cycle 1, Day 1). Perform urine or serum pregnancy test every three cycles thereafter. Confirm any positive urine pregnancy test with a serum pregnancy test. Patients with positive serum pregnancy tests should be discontinued from study drug.
- ^o Thyroid function testing (TH, free T3, free T4) will be performed at screening, Cycle 1, Day 1, and every three cycles thereafter.
- ^p Urinalysis by dipstick (specific gravity, pH, glucose, protein, ketones, and blood).
- ^q At screening, patients will be tested for HIV, HBsAg, total HBcAb, and HCV antibody. If a patient has a negative HBsAg test and a positive total HBcAb test at screening, an HBV DNA test should be performed. If a patient has a positive HCV antibody test at screening, an HCV RNA test must be performed to determine if the patient has an active HCV infection.
- ^r EGFR and ALK testing with approved test to be conducted at or prior to screening to rule out presence of EGFR-sensitizing mutations or ALK rearrangements. If either test is confirmed positive, the patient will be ineligible for enrollment (see Section 4.1.2 for exclusion criteria and Section 1.1.3 for NCCN guidelines on testing). For patients who are unable or unwilling to provide a tissue sample to determine EGFR status, the EGFR Cobas[®] plasma test is available. Please contact the Medical Monitor for additional options.
- ^s See [Appendix 2](#) for detailed schedule.

Appendix 1a Schedule of Activities

- ^t The optional RBR whole blood sample requires separate specific informed consent and the sample can be collected at any time during the course of the study.
- ^u Optional tissue biopsy specimen(s) may be submitted at any time prior to or during enrollment at the following timepoints: from the most recent diagnosis of metastatic NSCLC, during treatment, and/or at progression. The quality of the sample should be confirmed by a local pathologist and conform to the Foundation Medicine Pathology Review Process for Optimal Tissue Utilization.
- ^v The initial dose will be delivered over 60 (\pm 15) minutes. If the first infusion is well tolerated, all subsequent infusions may be delivered over 30 (\pm 10) minutes. Atezolizumab treatment may be continued until lack of clinical benefit, unacceptable toxicity, withdrawal of consent, patient or physician decision to discontinue treatment, or death.
- ^w CT scans (with oral/intravenous contrast unless contraindicated) or MRI scans of the chest and abdomen. A CT scan of the pelvis is required at screening and as clinically indicated or as per local standard of care at subsequent response evaluations. A CT (with contrast) or MRI scan of the head must be done at screening to evaluate CNS metastasis in all patients. See Section 4.5.5 for details. Perform tumor assessment at baseline and every 6 weeks (\pm 7 days) thereafter regardless of dose delays for the first 12 months following Cycle 1, Day 1. After 12 months, tumor assessment will be required every 9 weeks (\pm 7 days); tumor assessments will continue until disease progression per RECIST v1.1 or loss of clinical benefit, consent withdrawal, study discontinuation, study completion or death, whichever occurs first. Patients who discontinue treatment for reasons other than disease progression (e.g., toxicity) will continue scheduled tumor assessments until disease progression, withdrawal of consent, study discontinuation, study completion (i.e., end of study), or death, whichever occurs first. In the absence of disease progression, tumor assessments should continue regardless of whether patients start a new anti-cancer therapy, unless consent is withdrawn.
- ^x All serious adverse events and adverse events of special interest, regardless of relationship to study drug, will be reported until 90 days after the last dose of study drug or initiation of new anti-cancer therapy, whichever occurs first. All other adverse events, regardless of relationship to study drug, will be reported until 30 days after the last dose of study drug or initiation of new anti-cancer therapy, whichever occurs first. After this period, the investigator should report any serious adverse events or adverse events of special interest.
- ^y Survival follow-up should continue until at least 18 months following the start of the study for each patient and at end of study defined as 18 months after the last patient's C1D1, death, withdrawal of consent, the patient is lost to follow-up, or whichever occurs first.

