4.3.2 Dosage, Administration, and Compliance

The dose level of atezolizumab proposed to be tested in this study is 1200 mg (equivalent to an average body weight–based dose of 15 mg/kg) administered by IV infusion every 21 (± 3) days.

Administration of atezolizumab will be performed in a setting with emergency medical facilities and staff who are trained to monitor for and respond to medical emergencies.

The initial dose of atezolizumab will be delivered via IV infusion over 60 (± 15) minutes. If the first infusion is tolerated without infusion-associated adverse events, the second infusion may be delivered over 30 (± 10) minutes. If the 30-minute infusion is well tolerated, all subsequent infusions may be delivered over 30 (± 10) minutes. For all infusions, vital signs will be assessed per the local standard of care (see [Appendix 1](#)).

Dose modifications to atezolizumab are not permitted.

No premedication will be allowed for the first dose of atezolizumab. Premedication may be administered for Cycles ≥ 2 at the discretion of the treating physician. The management of infusion-related reactions will be according to severity as follows:

- In the event that a patient experiences a mild (NCI CTCAE Grade 1) infusion-related event, the infusion rate should be reduced to one-half the rate being given at the time of event onset. Once the event has resolved, the investigator should continue to deliver the infusion at the reduced rate for 30 minutes. If tolerated, the infusion rate may then be increased to the original rate.
- In the event that a patient experiences a moderate infusion-related event (NCI CTCAE Grade 2) or flushing, fever, or throat pain, the patient should have his or her infusion immediately interrupted and should receive aggressive symptomatic treatment. The infusion should be restarted only after the symptoms have adequately resolved to the baseline grade. The infusion rate at restart should be one-half of the rate that was in progress at the time of the onset of the infusion-related event.
- For severe or life-threatening infusion-related events (NCI CTCAE Grade 3 or 4), the infusion should be stopped immediately, and aggressive resuscitation and supportive measures should be initiated. Patients experiencing severe or

life-threatening infusion-related events will not receive further infusion and will be further managed as clinically indicated until the event resolves.

See [Appendix 5](#) for anaphylaxis precautions.

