Atezolizumab infusions will be administered per the instructions outlined in [Table 4](#).

Table 4 Administration of First and Subsequent Infusions of Atezolizumab

First Infusion	Subsequent Infusions

 • No premedication administered for atezolizumab specifically is permitted • Record patient’s vital signs (heart rate, respiratory rate, blood pressure, and temperature) within 60 minutes before starting infusion. • Infuse atezolizumab (1200 mg in a 250-mL 0.9% NaCl intravenous infusion bag) over 60 (\pm 15) minutes. • If clinically indicated, record patient’s vital signs (heart rate, respiratory rate, blood pressure, and temperature) during the infusion at 15, 30, 45, and 60 minutes (\pm 5-minute windows are allowed for all timepoints). • Record patient’s vital signs (heart rate, respiratory rate, blood pressure, and temperature) at 30 (\pm 10) minutes after the infusion. • Patients will be informed about the possibility of delayed post-infusion symptoms and instructed to contact their study physician if they develop such symptoms. 	
 • If patient experienced infusion-related reaction during any previous infusion, premedication with antihistamines may be administered for Cycles \geq 2 at the discretion of the treating physician. • Record patient’s vital signs (heart rate, respiratory rate, blood pressure, and temperature) within 60 minutes before starting infusion. • If the patient tolerated the first infusion well without infusion-associated adverse events, the second infusion may be delivered over 30 (\pm 10) minutes. • If no reaction occurs, subsequent infusions may be delivered over 30 (\pm 10) minutes. Continue to record vital signs within 60 minutes before starting infusion and during and after the infusion, if clinically indicated. • If the patient had an infusion-related reaction during the previous infusion, the subsequent infusion must be delivered over 60 (\pm 15) minutes. Record patient’s vital signs (heart rate, respiratory rate, blood pressure, and temperature) every 15 (\pm 5) minutes during the infusion if clinically indicated or patient experienced symptoms during the previous infusion. • Record patient’s vital signs (heart rate, respiratory rate, blood pressure, and temperature) 30 min (\pm 10 min) after the infusion if clinically indicated or patient experienced symptoms during previous infusion.

NaCl=sodium chloride.

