4.4.1 Permitted Therapy

Premedication with antihistamines may be administered for any atezolizumab infusions after Cycle 1.

Patients should continue use of maintenance therapy as follows:

- Hormonal therapy with gonadotropin-releasing hormone agonists or antagonists for prostate cancer
- Oral contraceptives
- Hormone-replacement therapy
- Prophylactic or therapeutic anticoagulation therapy (such as low-molecular-weight heparin or warfarin at a stable dose level)
- Palliative radiotherapy (e.g., treatment of known bony metastases), provided it does not interfere with the assessment of tumor target lesions (e.g., the lesion being irradiated is not the only site of disease, because that would render the patient not evaluable for response by tumor assessments according to RECIST v1.1)
 - It is not a requirement to withhold atezolizumab during palliative radiotherapy
- Inactive vaccinations, but not live, attenuated vaccinations, are permitted during the course of the study (i.e., only inactivated forms of the Influenza vaccinations are permitted). Live, attenuated vaccinations are prohibited (see Section 4.4.3).
- Megestrol administered as an appetite stimulant
- Inhaled corticosteroids for chronic obstructive pulmonary disease
- Mineralocorticoids (e.g., fludrocortisone)
- Low-dose corticosteroids for patients with orthostatic hypotension or adrenocortical insufficiency

In general, investigators should manage a patient's care with supportive therapies as clinically indicated per local standards. Patients who experience infusion-associated symptoms may be treated symptomatically with acetaminophen, ibuprofen, diphenhydramine, and/or famotidine or another H₂-receptor antagonist per standard practice. Serious infusion-associated events manifested by dyspnea, hypotension, wheezing, bronchospasm, tachycardia, reduced oxygen saturation, or respiratory distress should be managed with supportive therapies as clinically indicated (e.g., supplemental oxygen and β_2 -adrenergic agonists) see [Appendix 5](#).

All medications must be recorded on the appropriate Concomitant Medications eCRF.

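### After a Grade 1–2 reaction at Cycle 2 or later, Appendix 1a footnote v (and in some cases the Section 4.3.2 text) permits a 30-minute next infusion, while Table 4 requires 60 minutes

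*Protocol*

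**What the plan says.** The protocol gives the duration of later infusions in three places.

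- **Appendix 1a, footnote v** (attached to the study-drug row): "If the first infusion is well tolerated, all subsequent infusions may be delivered over 30" (±10) minutes. Nothing is said about a reaction at a later infusion.
- **Section 4.3.2, body text**: after a tolerated first infusion the second may be shortened, and then "If the 30-minute infusion is well tolerated, all subsequent infusions may be delivered over 30" (±10) minutes.
- **Section 4.3.2, Table 4**, subsequent infusions: "If the patient had an infusion-related reaction during the previous infusion, the subsequent infusion must be delivered over 60" (±15) minutes.

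Table 4 is introduced by the sentence "Atezolizumab infusions will be administered per the instructions outlined in" that table.

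Premedication appears in five places. The body text of Section 4.3.2 reads "No premedication will be allowed for the first dose of atezolizumab. Premedication may be administered for Cycles" ≥ 2, at the physician's discretion. Table 4 reads "If patient experienced infusion-related reaction during any previous infusion, premedication with antihistamines may be administered for Cycles" ≥ 2. Section 4.4.1 reads "Premedication with antihistamines may be administered for any atezolizumab infusions after Cycle 1", and the synopsis has the same sentence. Appendix 8 mentions antihistamines or antipyretics/analgesics for patients who reacted at Cycle 1.

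**The concern.** The three duration statements use different conditions. Footnote v looks back to the first infusion. The Section 4.3.2 text looks back to a tolerated 30-minute infusion. Table 4 looks back to the infusion just given. They agree while nothing happens, and they part company for the patient who has just reacted, which is the case in which a site most needs a single answer.

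A site that works from the schedule of activities could give the next infusion at the shorter duration and, in doing so, break a mandatory instruction elsewhere in the protocol. Neither the site nor the monitor could say with confidence whether that was a deviation. Infusion-reaction syndromes are events of special interest (Protocol Section 5.2.3), and SAP Section 4.6.2 summarises infusion-related reactions. The exposure summary in SAP Section 4.6.1 lists treatment duration, number of cycles and dose intensity but not infusion duration, so mixed practice would not show there.

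**Working it through.** There is no planned figure to reproduce. The check is to apply each passage to the same patient.

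**Inputs.** Dose 1200 mg; durations 60 (±15) and 30 (±10) minutes (Section 4.3.2, Table 4, footnote v).

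- Longer window: 60 − 15 = 45 to 60 + 15 = 75 minutes.
- Shorter window: 30 − 10 = 20 to 30 + 10 = 40 minutes.
- Gap between the windows: 45 − 40 = 5 minutes, so they do not overlap.
- Nominal rates: 1200/60 = 20 mg/min and 1200/30 = 40 mg/min, a factor of two.

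**Case A.** Cycle 1 is tolerated over 60 minutes, a Grade 1–2 reaction occurs at a 30-minute Cycle 2, and Cycle 3 is due.

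**Case B.** Cycle 1 and a 30-minute Cycle 2 are tolerated, a Grade 1–2 reaction occurs at Cycle 3, and Cycle 4 is due.

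| Passage | Case A, next infusion | Case B, next infusion |
|---|---|---|
| Table 4 | 45–75 min required | 45–75 min required |
| Footnote v | 20–40 min permitted | 20–40 min permitted |
| Section 4.3.2 text | 30-min permission not triggered | 20–40 min permitted |

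In Case A footnote v stands alone against Table 4, because the body text makes its permission depend on tolerating the 30-minute infusion. In Case B both footnote v and the body text permit what Table 4 excludes, so Section 4.3.2 also disagrees with its own table.

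**Scope.** Section 4.3.2 gives no further infusion after a Grade 3 or 4 reaction, and Appendix 8 allows re-challenge only with documented approval. The conflict therefore concerns Grade 1–2 reactions in patients who are dosed again.

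**Premedication from Cycle 2.**

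| Passage | Trigger | Agents named |
|---|---|---|
| Section 4.3.2 text | none | none |
| Synopsis, Section 4.4.1 | none | antihistamines |
| Table 4 | reaction at any previous infusion | antihistamines |
| Appendix 8 | reaction at Cycle 1 | antihistamines or antipyretics/analgesics |

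Every row grants permission and none withholds it.

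**The case against.** The best defence is that the protocol already shows which text to follow. Section 4.3.2 sends the site to Table 4 for administration, and footnote h of Appendix 1a refers to Section 4.3.2 for requirements during infusions. On that view footnote v is a summary, and a summary does not cancel a specific mandatory line in the designated table. This makes the error less likely, and it stands to that extent. It does not remove the conflict: neither sentence is a precedence rule, footnote h belongs to vital signs, footnote v carries no reference to Table 4, and the body text next to the table omits the exception too.

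Four stronger readings are tempting, and the documents do not support them.

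- *No infusion can satisfy both rules.* The windows are disjoint, but footnote v grants a permission while Table 4 imposes a requirement. Not using a permission breaks nothing, so a 60-minute infusion satisfies every passage. By the same token, footnote v does not direct that the patient receive 30 minutes.
- *Every patient who first reacts at Cycle 2 or later is affected.* Grade 3–4 reactors are not, apart from approved re-challenge.
- *The premedication rules contradict each other.* Table 4 does not confine antihistamines to patients who have reacted; it says they may be given in that case. The only prohibition concerns the first dose, and the text and Table 4 agree on it. Section 4.4.2 separately addresses systemic corticosteroids.
- *Differing durations distort the reported reaction incidence.* The duration rules diverge only once a patient has reacted. SAP Section 4.6.2 counts repeated occurrences of the same event once at maximum severity, so that patient is already counted and only the maximum grade could change.

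**Conclusion.** The duration conflict is real and should be corrected. For a patient who tolerates the first infusion and has a Grade 1–2 reaction at Cycle 2 or later, footnote v permits 30 (±10) minutes where Table 4 requires 60 (±15). The Section 4.3.2 text shares the gap when a 30-minute infusion has already been tolerated. An infusion given under that permission breaches Table 4; an infusion over 60 minutes breaches nothing.

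The size is modest. The documents give no infusion-reaction rate for this study, so the number of patients affected cannot be stated. Response rate, progression-free survival, power and error rates are untouched, and the safety summaries are descriptive. The reason to act is that the gap concerns patients who have just reacted and is cheap to close. The conclusion rests on reading footnote v literally and on the absence of a stated order of precedence between the schedule and Section 4.3.2. The premedication differences are a minor, secondary matter of trigger and named agents.

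**What to change.** Reconcile footnote v and the Section 4.3.2 text with Table 4 so that one condition governs the duration of each later infusion. Alternatively, replace the duration wording in footnote v with a cross-reference to Table 4; the body text of Section 4.3.2 would still need to be aligned with the table. Which condition stands is for the sponsor's clinical team to decide; this review takes no position on it.

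In the same amendment, harmonise the premedication statements in the synopsis, Section 4.3.2, Section 4.4.1, Table 4 and Appendix 8 so that the trigger and the named agents match.

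The cost is wording in one footnote and a few sections. Protocol Section 9.6 sends amendments to the institutional review board or ethics committee, so the change is best carried by the next planned amendment. No SAP change is required.

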Appendix 1b
Optional Long-Term Follow-Up Schedule of Assessments

Activity	All Treatment Cycles	Treatment Completion/DC b,c	Safety Follow-Up (Phone Call)	Overall Survival Follow-Up (Phone Call)	Study Completion/DC
	Continued dosing Every 21 (±3) Days ^a		30 days post-last treatment	Every 3 months for the first year, then every 6 months thereafter, or up to 5 years from enrollment of the first patient into the study until the last patient dies, withdraws consent, is lost to follow-up, whichever occurs first	
Study drug administration	x				
Adverse Event	x	x	x		
Survival Information				x	x

DC=discontinuation
 
^a Patients on study drug will continue therapy until they have received a total of 2 years of atezolizumab treatment (32 cycles).
 
^b Patients will be asked to return to the clinic no more than 30 days after the last dose for a treatment discontinuation visit. Note that the Study Discontinuation eCRF should not be completed until after the patient has discontinued from the study.
 
^c Patients who complete the optional long-term follow-up study will return to the clinic for a study completion visit within 30 days following study completion. Patients who discontinue the study prematurely will return to the clinic for a study discontinuation visit within 30 days following discontinuation from the study.
					

Appendix 2 Schedule of Biomarker Samples

Visit	Timepoint	Sample Type	Proposed Biomarkers	Mandatory/Optional
Screening (Day -28 to Day -1)	NA	Plasma	bTMB	Mandatory
Baseline (Day 1 of Cycle 1)	Prior to infusion	Plasma	bTMB	Mandatory
Baseline (Day 1 of Cycle 1)	Prior to infusion	PBMC	Immune gene expression	Mandatory
Day 1 of Cycle 2	Prior to infusion	Plasma	bTMB	Mandatory
Day 1 of Cycle 2	Prior to infusion	PBMC	Immune gene expression	Mandatory
Day 1 of Cycle 3	Prior to infusion	Plasma	bTMB	Optional
Day 1 of Cycle 4	Prior to infusion	Plasma	bTMB	Mandatory
During treatment	At radiographic progression or loss of clinical benefit	Plasma	bTMB	Mandatory
During treatment	At radiographic progression or loss of clinical benefit	PBMC	Immune gene expression	Mandatory
NA	Anytime during study	Tissue	tTMB and somatic alterations	Optional

bTMB = blood tumor mutational burden; NA = not applicable; PBMC = peripheral blood mononuclear cells; tTMB = tissue tumor mutational burden.

Appendix 3

IASLC Lung Cancer Staging Project Proposed for the Eighth Edition of the American Joint Committee on Cancer Non–Small Cell Lung Cancer Staging System¹

T: Primary tumor	
Tx	Primary tumor cannot be assessed or tumor proven by presence of malignant cells in sputum or bronchial washings but not visualized by imaging or bronchoscopy
T0	No evidence of primary tumor
Tis	Carcinoma in situ
T1	Tumor ≤ 3 cm in greatest dimension surrounded by lung or visceral pleura without bronchoscopic evidence of invasion more proximal than the lobar bronchus (i.e., not in the main bronchus) ^a
T1a(mi)	Minimally invasive adenocarcinoma^b
T1a	Tumor ≤ 1 cm in greatest dimension ^b
T1b	Tumor >1 cm but ≤ 2 cm in greatest dimension ^b
T1c	Tumor >2 cm but ≤ 3 cm in greatest dimension ^b
T2	Tumor >3 cm but ≤ 5 cm or tumor with any of the following features ^c : 
 - Involves main bronchus regardless of distance from the carina but without involvement of the carina - Invades visceral pleura - Associated with atelectasis or obstructive pneumonitis that extends to the hilar region, involving part or all of the lung
T2a	Tumor >3 cm but ≤ 4 cm in greatest dimension
T2b	Tumor >4 cm but ≤ 5 cm in greatest dimension
T3	Tumor >5 cm but ≤ 7 cm in greatest dimension or associated with separate tumor nodule(s) in the same lobe as the primary tumor or directly invades any of the following structures: chest wall (including the parietal pleura and superior sulcus tumors), phrenic nerve, parietal pericardium
T4	Tumor >7 cm in greatest dimension or associated with separate tumor nodule(s) in a different ipsilateral lobe than that of the primary tumor or invades any of the following structures: diaphragm, mediastinum, heart, great vessels, trachea, recurrent laryngeal nerve, esophagus, vertebral body, and carina
N: Regional lymph node involvement	
Nx	Regional lymph nodes cannot be assessed
N0	No regional lymph node metastasis
N1	Metastasis in ipsilateral peribronchial and/or ipsilateral hilar lymph nodes and intrapulmonary nodes, including involvement by direct extension
N2	Metastasis in ipsilateral mediastinal and/or subcarinal lymph node(s)
N3	Metastasis in contralateral mediastinal, contralateral hilar, ipsilateral or contralateral scalene, or supraclavicular lymph node(s)
M: Distant metastasis	
M0	No distant metastasis
M1	Distant metastasis present
M1a	Separate tumor nodule(s) in a contralateral lobe; tumor with pleural or pericardial nodule(s) or malignant pleural or pericardial effusion ^d
M1b	Single extrathoracic metastasis ^e
M1c	Multiple extrathoracic metastases in one or more organs

Note: Changes to the seventh edition are in bold.
 
^aThe uncommon superficial spreading tumor of any size with its invasive component limited to the bronchial wall, which may extend proximal to the main bronchus, is also classified as T1a.
 
^bSolitary adenocarcinoma, ≤ 3 cm with a predominately lepidic pattern and ≤ 5 mm invasion in any one focus.
 
^cT2 tumors with these features are classified as T2a if ≤ 4 cm in greatest dimension or if size cannot be determined, and T2b if >4 cm but ≤ 5 cm in greatest dimension.
 
^dMost pleural (pericardial) effusions with lung cancer are due to tumor. In a few patients, however, multiple microscopic examinations of pleural (pericardial) fluid are negative for tumor and the fluid is nonbloody and not an exudate. When these elements and clinical judgment dictate that the effusion is not related to the tumor, the effusion should be excluded as a staging descriptor.
 
^eThis includes involvement of a single distant (nonregional) lymph node.
	

Appendix 3

IASLC Lung Cancer Staging Project Proposed for the Eighth Edition of the American Joint Committee on Cancer Non–Small Cell Lung Cancer Staging System¹ (cont.)

Descriptor in 7th edition	Proposed T/M	N categories			
		Overall stage			
		N0	N1	N2	N3
T1 ≤ 1 cm	T1a	IA1 (IA)	IB (IIA)	IIIA	IIIB
T1 > 1-2 cm	T1b	IA2 (IA)	IB (IIA)	IIIA	IIIB
T1 > 2-3 cm	T1c	IA3 (IA)	IB (IIA)	IIIA	IIIB
T2 > 3-4 cm	T2a	IB	IB (IIA)	IIIA	IIIB
T2 > 4-5 cm	T2b	IIA (IB)	IB (IIA)	IIIA	IIIB
T2 > 5-7 cm	T3	IIB (IIA)	IIA (IIB)	IIIB (IIIA)	IIIC (IIIB)
T3 structures	T3	IIB	IIA	IIIB (IIIA)	IIIC (IIIB)
T3 > 7 cm	T4	IIIA (IIB)	IIA	IIIB (IIIA)	IIIC (IIIB)
T3 diaphragm	T4	IIIA (IIB)	IIA	IIIB (IIIA)	IIIC (IIIB)
T3 endobronchial: location/atelectasis 3-4 cm	T2a	IB (IIB)	IB (IIIA)	IIIA	IIIB
T3 endobronchial: location/atelectasis 4-5 cm	T2b	IIA (IIB)	IB (IIIA)	IIIA	IIIB
T4	T4	IIIA	IIIA	IIIB	IIIC (IIIB)
M1a	M1a	IVA (IV)	IVA (IV)	IVA (IV)	IVA (IV)
M1b single lesion	M1b	IVA (IV)	IVA (IV)	IVA (IV)	IVA (IV)
M1c multiple lesions	M1c	IVB (IV)	IVB (IV)	IVB (IV)	IVB (IV)

^aWhere there is a change, the resultant stage groupings proposed for the eighth edition are in bold, and the stage in the seventh edition is given in parenthesis.
T, tumor; M, metastasis.

¹ Goldstraw P, Chansky K, Crowley J, et al. The IASLC Lung Cancer Staging Project: Proposals for Revision of the TNM Stage Groupings in the Fourthcoming (Eighth) Edition of the TNM Classification for Lung Cancer. J Thorac Onc 2015;11(1): 39-51.

Appendix 4

Response Evaluation Criteria in Solid Tumors (RECIST): Excerpt from Original Publication

Selected sections from the Response Evaluation Criteria in Solid Tumors (RECIST), Version 1.1¹ are presented below, with slight modifications and the addition of explanatory text as needed for clarity.²

MEASURABILITY OF TUMOR AT BASELINE

DEFINITIONS

At baseline, tumor lesions/lymph nodes will be categorized measurable or nonmeasurable as follows:

Measurable Tumor Lesions

Tumor Lesions. Tumor lesions must be accurately measured in at least one dimension (longest diameter in the plane of measurement is to be recorded) with a minimum size of:

- 10 mm by computed tomography (CT) or magnetic resonance imaging (MRI) scan (CT/MRI scan slice thickness/interval no greater than 5 mm)
- 10-mm caliper measurement by clinical examination (lesions that cannot be accurately measured with calipers should be recorded as nonmeasurable)
- 20 mm by chest X-ray

Malignant Lymph Nodes. To be considered pathologically enlarged and measurable, a lymph node must be ≥ 15 mm in the short axis when assessed by CT scan (CT scan slice thickness recommended to be no greater than 5 mm). At baseline and in follow-up, only the short axis will be measured and followed. See also notes below on “Baseline Documentation of Target and Nontarget Lesions” for information on lymph node measurement.

Nonmeasurable Tumor Lesions

Nonmeasurable tumor lesions encompass small lesions (longest diameter < 10 mm or pathological lymph nodes with ≥ 10 to < 15 mm short axis), as well as truly nonmeasurable lesions. Lesions considered truly nonmeasurable include leptomeningeal disease, ascites, pleural or pericardial effusion, inflammatory breast disease, lymphangitic involvement of skin or lung, peritoneal spread, and abdominal masses/abdominal organomegaly identified by physical examination that is not measurable by reproducible imaging techniques.

¹ Eisenhauer EA, Therasse P, Bogaerts J, et al. New response evaluation criteria in solid tumors: Revised RECIST guideline (Version 1.1). *Eur J Cancer* 2009;45:228–47.

² For consistency within this document, the section numbers and cross-references to other sections within the article have been deleted and minor formatting changes have been made.

Appendix 4

Response Evaluation Criteria in Solid Tumors (RECIST): Excerpt from Original Publication (cont.)

Special Considerations Regarding Lesion Measurability

Bone lesions, cystic lesions, and lesions previously treated with local therapy require particular comment, as outlined below.

Bone lesions:

- Bone scan, positron emission tomography (PET) scan, or plain films are not considered adequate imaging techniques to measure bone lesions. However, these techniques can be used to confirm the presence or disappearance of bone lesions. When a bone scan is the sole indicator of progression, progression in bone will be defined as when at least two or more new lesions are seen on bone scan compared with screening. In situations where the scan findings are suggestive of a flare reaction, or apparent new lesion(s) which may represent trauma, these results must be confirmed with other imaging modalities such as MRI or fine-cut CT to constitute progression. Only a single new bone lesion on bone scan is required for progression if the lesion can be correlated on CT, MRI or plain film.
- Lytic bone lesions or mixed lytic-blastic lesions, with identifiable soft tissue components, that can be evaluated by cross-sectional imaging techniques such as CT or MRI can be considered measurable lesions if the soft tissue component meets the definition of measurability described above.
- Blastic bone lesions are nonmeasurable.

Cystic lesions:

- Lesions that meet the criteria for radiographically defined simple cysts should not be considered malignant lesions (neither measurable nor nonmeasurable) since they are, by definition, simple cysts.
- Cystic lesions thought to represent cystic metastases can be considered measurable lesions if they meet the definition of measurability described above. However, if noncystic lesions are present in the same patient, these are preferred for selection as target lesions.

Lesions with prior local treatment:

- Tumor lesions situated in a previously irradiated area, or in an area subjected to other loco-regional therapy, are usually not considered measurable unless there has been demonstrated progression in the lesion. Study protocols should detail the conditions under which such lesions would be considered measurable.

Appendix 4

Response Evaluation Criteria in Solid Tumors (RECIST): Excerpt from Original Publication (cont.)

TARGET LESIONS: SPECIFICATIONS BY METHODS OF MEASUREMENTS

Measurement of Lesions

All measurements should be recorded in metric notation, with use of calipers if clinically assessed. All baseline evaluations should be performed as close as possible to the treatment start and never more than 4 weeks before the beginning of the treatment.

Method of Assessment

The same method of assessment and the same technique should be used to characterize each identified and reported lesion at baseline and during study. Imaging-based evaluation should always be the preferred option.

Clinical Lesions. Clinical lesions will only be considered measurable when they are superficial and ≥ 10 mm in diameter as assessed using calipers (e.g., skin nodules). For the case of skin lesions, documentation by color photography, including a ruler to estimate the size of the lesion, is suggested.

Chest X-Ray. Chest CT is preferred over chest X-ray, particularly when progression is an important endpoint, since CT is more sensitive than X-ray, particularly in identifying new lesions. However, lesions on chest X-ray may be considered measurable if they are clearly defined and surrounded by aerated lung.

CT, MRI. CT is the best currently available and reproducible method to measure lesions selected for response assessment. This guideline has defined measurability of lesions on CT scan based on the assumption that CT slice thickness is 5 mm or less. When CT scans have slice thickness greater than 5 mm, the minimum size for a measurable lesion should be twice the slice thickness. MRI is also acceptable.

If prior to enrollment it is known that a patient is unable to undergo CT scans with intravenous (IV) contrast because of allergy or renal insufficiency, the decision as to whether a noncontrast CT or MRI (without IV contrast) will be used to evaluate the patient at baseline and during the study should be guided by the tumor type under investigation and the anatomic location of the disease. For patients who develop contraindications to contrast after baseline contrast CT is done, the decision as to whether noncontrast CT or MRI (enhanced or nonenhanced) will be performed should also be based on the tumor type and the anatomic location of the disease and should be optimized to allow for comparison with the prior studies if possible. Each case should be discussed with the radiologist to determine if substitution of these other approaches is possible and, if not, the patient should be considered not evaluable from that point forward. Care must be taken in measurement of target lesions on a different modality

Appendix 4

Response Evaluation Criteria in Solid Tumors (RECIST): Excerpt from Original Publication (cont.)

and interpretation of nontarget disease or new lesions since the same lesion may appear to have a different size with use of a new modality.

Ultrasound. Ultrasound is not useful in the assessment of lesion size and should not be used as a method of measurement.

Endoscopy, Laparoscopy, Tumor Markers, Cytology, Histology. The utilization of these techniques for objective tumor evaluation cannot generally be advised.

TUMOR RESPONSE EVALUATION

ASSESSMENT OF OVERALL TUMOR BURDEN AND MEASURABLE DISEASE

To assess objective response or future progression, it is necessary to estimate the overall tumor burden at baseline and to use this as a comparator for subsequent measurements. Measurable disease is defined by the presence of at least one measurable lesion, as detailed above.

BASELINE DOCUMENTATION OF TARGET AND NONTARGET LESIONS

When more than one measurable lesion is present at baseline, all lesions up to a maximum of five lesions total (and a maximum of two lesions per organ) representative of all involved organs should be identified as target lesions and will be recorded and measured at baseline. This means in instances where patients have only one or two organ sites involved, a maximum of two lesions (one site) and four lesions (two sites), respectively, will be recorded. Other lesions (albeit measurable) in those organs will be recorded as nonmeasurable lesions (even if the size is > 10 mm by CT scan).

Target lesions should be selected on the basis of their size (lesions with the longest diameter) and be representative of all involved organs, but additionally, should lend themselves to reproducible repeated measurements. It may be the case that, on occasion, the largest lesion does not lend itself to reproducible measurement, in which circumstance the next largest lesion that can be measured reproducibly should be selected.

Lymph nodes merit special mention since they are normal anatomical structures that may be visible by imaging even if not involved by tumor. As noted above, pathological nodes that are defined as measurable and may be identified as target lesions must meet the criterion of a short axis of ≥ 15 mm by CT scan. Only the short axis of these nodes will contribute to the baseline sum. The short axis of the node is the diameter normally used by radiologists to judge if a node is involved by solid tumor. Nodal size is normally reported as two dimensions in the plane in which the image is obtained (for CT scan, this

Appendix 4

Response Evaluation Criteria in Solid Tumors (RECIST): Excerpt from Original Publication (cont.)

is almost always the axial plane; for MRI the plane of acquisition may be axial, sagittal, or coronal). The smaller of these measures is the short axis. For example, an abdominal node that is reported as being 20 mm × 30 mm has a short axis of 20 mm and qualifies as a malignant, measurable node. In this example, 20 mm should be recorded as the node measurement. All other pathological nodes (those with short axis ≥ 10 mm but < 15 mm) should be considered nontarget lesions. Nodes that have a short axis < 10 mm are considered nonpathological and should not be recorded or followed.

